8.4.22 Treatment Satisfaction Questionnaire – Medication-9

The TSQM-9 is an abbreviated 9-item version of the TSQM, excluding the side effects of medication domain. The domains included in the TSQM-9 include effectiveness (3 items), convenience (3 items) and global satisfaction (3 items). The TSQM-9 domain scores range from 0 to 100 with higher scores representing higher satisfaction.

The scores for each measure are as follows:

- Global Satisfaction:
 - If no items are missing: $([\text{Sum}(\text{Item 7 to Item 9}) - 3]/14) * 100$
 - If either Item 7 or 8 is missing: $([\text{Sum}(\text{the two completed items})] - 2)/10 * 100$
 - If Item 9 is missing: $([\text{Sum}(\text{Item 7 and Item 8})] - 2)/8 * 100$
- Effectiveness
 - If no items are missing: $([\text{Item 1} + \text{Item 2} + \text{Item 3}] - 3)/18 * 100$

- If one item is missing: $\left(\frac{\text{Sum}(\text{the two completed items}) - 2}{12}\right) * 100$
- Convenience
 - If no items are missing: $\left(\frac{\text{Sum}(\text{Item 4 to Item 6}) - 3}{18}\right) * 100$
 - If one item is missing: $\left(\frac{\text{Sum}(\text{the two completed items}) - 2}{12}\right) * 100$

Frequency tables will be produced to summarize answers provided to each of the 9 items of the TSQM-9 at Weeks 16 and 48 by treatment group. Responses to TSQM-9 will be summarized based on OC. No imputation will be applied.

The number and percentage of participants that complete the TSQM-9 will be calculated for each visit by treatment group. The percentage will be based on the number of participants in the RS. The summary will be repeated where the percentage is based on the subset of participants who complete each particular visit. A participant will be considered a completer at a visit if each of the domains are completed at that visit.

A by-participant listing of TSQM-9 will be provided.

8.4.23 Lesion intervention

Investigators will have the option to perform interventions in the event an acutely painful lesion occurs that requires immediate intervention.

The following rules will be used to assign a lesion intervention to a study period:

- **Initial Treatment Period:** a lesion intervention will be assigned to the Initial Treatment Period if it has been performed between the first administration of IMP on Day 1 up to and including Week 16.
- **Maintenance Treatment Period:** a lesion intervention will be assigned to the Maintenance Treatment Period if it has been performed between Week 16 through the Week 48 visit.

Methods for dealing with partial dates are specified in Section 4.2.4.

A listing of participants who receive any lesion intervention will be provided.

The number and percentage of participants who receive at least 1 lesion intervention will be summarized by treatment group for the Initial Treatment Period, Maintenance Treatment Period, and the combined Initial and Maintenance Treatment Period.

The number and percentage of participants with 2, 3, and 4 or more lesion interventions will also be summarized by treatment group for the Initial Treatment Period, Maintenance Treatment Period, and the combined Initial and Maintenance Treatment Period.

The number and percentage of participants with 2 or more lesion interventions performed on the same lesion will be summarized by treatment group for the Initial Treatment Period, Maintenance Treatment Period, and the combined Initial and Maintenance Treatment Period.

8.5 Additional statistical analyses of other efficacy endpoints

For selected other efficacy variables, it is of interest to perform statistical tests and to calculate inferential statistics. As these tests are not part of the multiplicity-controlled procedure, the associated p-values are considered nominal and are not controlled for multiplicity.

For binary variables, the analysis will follow what was specified for the primary analysis of the primary endpoint and the corresponding p-value reported. Missing values will be imputed as for the primary analysis. For continuous variables, the MI – MCMC / Monotone Regression approach used for the secondary continuous endpoint will be applied for the imputation model. The analysis model will be as for the corresponding secondary continuous endpoint analysis, unless otherwise indicated.

Below is a list of variables for which these nominal p-values will be calculated. The results of these inferential tests will be presented in a single table summarizing the testing performed outside of the multiplicity-controlled testing procedure.

All tests will be for both ██████████ vs Placebo and ██████████ vs Placebo (tested separately) and will be performed for the Week 12 and Week 16 visits only. If the Week 16 visit test is already part of the controlled testing procedure in the primary or secondary analyses, only Week 12 is indicated here.

- HiSCR₅₀ at Week 12
- HiSCR₇₅ at Week 12
- HiSCR₉₀
- HiSCR₁₀₀
- Flare by Week 12
- Time to flare by Week 12 (based on time-to-event analysis per Section 8.4.4 and adjusted appropriately)
- IHS4 change from Baseline
- IHS4 percentage change from Baseline
- HS Physician's Global Assessment: rate of participants who are Clear or Mild
- DLQI total score change from Baseline at Week 12
- Worst Skin Pain per HSSDD change from Baseline at Week 12
- Skin Pain response per HSSDD at Week 12

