8.4.7 HS-Physician's Global Assessment 6-point scale

The HS-Physician's Global Assessment is a validated 6-point scale that is used to measure improvement in inflammatory nodules, abscesses, and draining tunnels. The HS-Physician's Global Assessment scale is defined in Table 8-4.

Table 8-4: HS-Physician's Global Assessment 6-point scale

Score	Rating	Description
0	Clear	No abscesses, no draining tunnels (fistulas/sinus tracts), no nodules
1	Minimal	No abscesses, no draining tunnels (fistulas/sinus tracts), no inflammatory nodules, presence of non-inflammatory nodules

Table 8–4: HS-Physician's Global Assessment 6-point scale

Score	Rating	Description
2	Mild	No abscesses or draining tunnels (fistulas/sinus tracts), and less than 5 inflammatory nodules, or Single abscess or draining tunnel (fistula/sinus tract), and no inflammatory nodules
3	Moderate	No abscesses or draining tunnels (fistulas/sinus tracts), and at least 5 inflammatory nodules, or Single abscess or draining tunnel (fistula/sinus tract) in the presence of inflammatory nodules, or Between 2 and 5 abscesses or draining tunnels (fistulas/sinus tracts) with or without inflammatory nodules, up to 10
4	Severe	Between 2 and 5 abscesses and draining tunnels (fistulas/sinus tracts), with inflammatory nodules that are greater than 10
5	Very severe	More than 5 abscesses or draining tunnels (fistulas/sinus tracts)

The gradings will be derived on a participant-level basis (ie, across all anatomical regions) based on the following rules:

- Clear:
 - number of abscesses = 0;
 - number of draining tunnels (fistulas/sinus tracts) = 0;
 - number of inflammatory nodules = 0;
 - number of non-inflammatory nodules = 0;
 - number of non-draining tunnels (fistulas/sinus tracts) – no limit;
 - number of HS scars – no limit;
- Minimal:
 - number of abscesses = 0;
 - number of draining tunnels (fistulas/sinus tracts) = 0;
 - number of inflammatory nodules = 0;
 - number of non-inflammatory nodules ≥ 1 ;
 - number of non-draining tunnels (fistulas/sinus tracts) – no limit;
 - number of HS scars – no limit;
- Mild:
 - number of abscesses = 0;
 - number of draining tunnels (fistulas/sinus tracts) = 0;

- number of inflammatory nodules ≥ 1 and ≤ 4 ;
- number of non-inflammatory nodules – no limit;
- number of non-draining tunnels (fistulas/sinus tracts) – no limit;
- number of HS scars – no limit;

OR

- sum of number of abscesses and number of draining tunnels (fistulas/sinus tracts) = 1;

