- number of inflammatory nodules = 0;
- number of non-inflammatory nodules – no limit;
- number of non-draining tunnels (fistulas/sinus tracts) – no limit;
- number of HS scars – no limit;

- Moderate:

- number of abscesses = 0;
- number of draining tunnels (fistulas/sinus tracts) = 0;
- number of inflammatory nodules ≥ 5 ;
- number of non-inflammatory nodules – no limit;
- number of non-draining tunnels (fistulas/sinus tracts) – no limit;
- number of HS scars – no limit;

OR

- sum number of abscesses and number of draining tunnels (fistulas/sinus tracts) = 1;
- number of inflammatory nodules ≥ 1 ;
- number of non-inflammatory nodules – no limit;
- number of non-draining tunnels (fistulas/sinus tracts) – no limit;
- number of HS scars – no limit;

OR

- sum of number of abscesses and number of draining tunnels (fistulas/sinus tracts) ≥ 2 and ≤ 5 ;
- number of inflammatory nodules ≤ 10 ;
- number of non-inflammatory nodules – no limit;
- number of non-draining tunnels (fistulas/sinus tracts) – no limit;
- number of HS scars – no limit;

- Severe:

- sum of number of abscesses and number of draining tunnels (fistulas/sinus tracts) ≥ 2 and ≤ 5 ;
- number of inflammatory nodules > 10 ;
- number of non-inflammatory nodules – no limit;
- number of non-draining tunnels (fistulas/sinus tracts) – no limit;
- number of HS scars – no limit;
- Very Severe:
 - sum of number of and number of draining tunnels (fistulas/sinus tracts) > 5 ;
 - number of inflammatory nodule – no limit;
 - number of non-inflammatory nodules – no limit;
 - number of non-draining tunnels (fistulas/sinus tracts) – no limit;
 - number of HS scars – no limit

The number and percentage of participants at each level of the assessment scale (Clear, Minimal, Mild, Moderate, Severe and Very severe) will be presented by treatment group and visit. The denominator for the percentages will be based on the number of participants in the given treatment group and visit for which there are no missing data for the HS-Physician's Global Assessment.

Shift tables for the changes from Baseline in this scale will be presented for each post-Baseline visit by treatment group. The denominator for the percentages will be based on the number of participants in the given treatment group and visit for which there is no missing data for the change from Baseline in HS-Physician's Global Assessment.

The HS-Physician's Global Assessment will be listed by treatment group and participant at each visit.

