- **Pre ADA_b positive – treatment-emergent reduced ADA_b (Category 3):** Includes study participants who are ADA_b positive at Baseline, and ADA_b negative at all sampling points post-Baseline during the period of interest.
- **Pre ADA_b positive – treatment-emergent unaffected ADA_b positive (Category 4):** Includes study participants who are ADA_b positive at Baseline and are ADA_b positive at any sampling point post-Baseline during the period of interest with titer values of the same magnitude as Baseline (ie, less than a predefined fold difference from the Baseline titer).
 - For this analysis, this is set at an increase of less than the validated Minimum Significant Ratio (MSR) of 2.07-fold from Baseline.
- **Pre ADA_b positive – treatment-emergent ADA_b boosted positive (Category 5):** Includes study participants who ADA_b positive at Baseline and are ADA_b positive at any sampling point post-Baseline during the period of interest with increased titer values compared to Baseline (equal to or greater than a predefined fold difference increase from Baseline titer which will be defined within the validation of the assay).
 - For this analysis, this is set at an increase equal to or greater than the validated MSR of 2.07-fold from Baseline.
 - Note: for any study participant who is ADA_b positive at Baseline and ADA_b positive at a post-Baseline time point during the period of interest, but for whom titers are not available to determine treatment unaffected or treatment boosted status, the study participant will be considered as treatment boosted, assuming no other samples are available.
- **ADA_b Inconclusive (Category 6):** Includes study participants who have an ADA_b positive Baseline (pre-treatment) sample and some post-Baseline samples during the period of interest are missing or inconclusive, while other post-Baseline samples are ADA_b negative.
- **Total treatment-emergent ADA_b positivity (Category 7 [Categories 2 and 5 combined]):** Includes study participants who are pre ADA_b negative – treatment-emergent ADA_b positive (Category 2) and pre ADA_b positive – treatment boosted ADA_b positive (Category 5).
- **Total prevalence of pre- ADA_b positivity (Category 8 [Categories 3, 4, 5 and 6 combined]):** Study participants that are tested ADA_b positive at Baseline.

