- The prevalence of immunogenicity, separated by treatment group, and defined subcategory, will be reported by visit, defined as (cumulative) proportion of participants having confirmed positive ADAb samples at any visit up to and including that visit. Missing samples will not be included in the denominator.
- The time to achieving treatment-emergent ADAb positivity, separated by treatment group and defined subcategory, will be analyzed based on Kaplan-Meier methods. This will be shown only for Categories 2 and 8 above. Participants will be considered to have an event at the time point at which treatment emergent ADAb positive is first achieved (taking the MSR into consideration for sub-category 5). Participants classified as treatment-emergent ADAb negative will be censored at the time of the last available ADAb result.
- A summary of HiSCR₅₀ responders at Week 16, separated by treatment group, as a function of ADAb titer will be presented graphically.
- Individual plots of plasma bimekizumab concentrations/ ADAb titer both plotted on the Y-axes by visit (x-axis) for the full treatment period (excluding SFU for interim analyses and

including SFU for final analyses) will be presented for participants with and without HiSCR₅₀ response at Week 16.

- Spaghetti plots of ADA_b titer (y-axis) by visit (x-axis), separated by treatment group for all ADA_b positive participants, including Baseline positive participants.
- Box plots of ADA_b titer (logscale) by time to first ADA_b positivity by treatment group.

The groups for defining ADA_b status for safety subgroup analyses are as follows:

- AEs starting before first ADA_b positive result
- AEs starting on or after first ADA_b positive result
- AEs for participants who were always ADA_b negative

This is further explained in Section 10.2.2

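### Two category slips in the SAP: the PGA responder in Section 8.5 skips Minimal, and the treatment-emergent antibody curve in Section 9.3.2 names Category 8 where Category 7 fits

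*SAP*

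**What the plan says.** **PGA.** SAP Section 8.5 lists variables that get nominal p-values for each of two bimekizumab dose regimens against placebo at Weeks 12 and 16. One entry is the PGA "rate of participants who are Clear or Mild". As a binary variable it takes the primary endpoint's logistic model and imputation. Section 8.4.7 reports "each level of the assessment scale (Clear, Minimal, Mild, Moderate, Severe and Very severe") by treatment group and visit, and Table 8–4 scores these levels 0 to 5 in that order. Minimal (score 1) is "No abscesses, no draining tunnels (fistulas/sinus tracts), no inflammatory nodules, presence of non-inflammatory nodules". Mild (score 2) is "No abscesses or draining tunnels (fistulas/sinus tracts), and less than 5 inflammatory nodules, or Single abscess or draining tunnel (fistula/sinus tract), and no inflammatory nodules". Section 8.4.7 defines no PGA responder.

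**Antibodies.** Section 9.3.2 states: "The time to achieving treatment-emergent ADAb positivity, separated by treatment group and defined subcategory, will be analyzed based on Kaplan-Meier methods". It then adds: "This will be shown only for Categories 2 and 8 above". In the same section, Category 7 is total treatment-emergent positivity (Categories 2 and 5 combined), and total pre-treatment positivity is "Category 8 [Categories 3, 4, 5 and 6 combined"]. The event rule refers to the minimum significant ratio for sub-category 5. The censoring rule covers only participants classified as treatment-emergent antibody negative, who are censored at their last available result.

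**The concern.** In both places the text names a category that does not match what is being measured.

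The PGA set leaves out the level between its two responder levels, so response is not monotone in severity. A participant who improves from Mild to Minimal loses response. The grade is derived by program from lesion counts, so the phrase can be coded exactly as written. If the programmer departs from it, the plan does not say which cut to use, and a choice made after unblinding would be post hoc.

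The antibody analysis is about positivity that emerges on treatment, but one of the two groups named is defined by positivity before treatment. Literal programming would give a curve whose title and population disagree, with most of its constituent categories given no event or censoring status.

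**Working it through.** There is no sample size, power or alpha figure to reproduce. The check sets the SAP's definitions against each other.

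**1. PGA.** Applying the grading rules of Section 8.4.7 to four lesion profiles, with all other lesion types that affect the grade at zero:

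| Profile | Score | In the set {0, 2}? |
|---|---|---|
| No lesions | 0 Clear | yes |
| 1 non-inflammatory nodule only | 1 Minimal | no |
| 4 inflammatory nodules only | 2 Mild | yes |
| 1 abscess only | 2 Mild | yes |

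The second profile is milder than the third and fourth, yet it is the only failure.

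Size of the error, with p0, p1 and p2 the shares of an arm at Clear, Minimal and Mild:

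- Rate as written: p0 + p2.
- If {0, 1, 2} was intended: the rate should be p0 + p1 + p2, so the error is −p1.
- If {0, 1} was intended: the rate should be p0 + p1, so the error is p2 − p1.

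The SAP gives no PGA shares, so the figures here are assumptions. Minimal shares of 2%, 5% and 10% give understatements of 2, 5 and 10 points against {0, 1, 2}. Against {0, 1}, a Mild share of 10% with a Minimal share of 2% gives +8 points (10 − 2), and the reverse gives −8 (2 − 10). The direction is therefore unknown until the intended cut is stated.

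Number of results affected: 2 regimens × 2 visits = 4 nominal comparisons.

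**2. Antibodies.** Category sets from Section 9.3.2:

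- Category 7 (total treatment-emergent positive) = {2, 5}.
- Category 8 (Baseline positive) = {3, 4, 5, 6}.
- Named for the analysis: {2} together with Category 8 = {2, 3, 4, 5, 6}.
- Named but not treatment-emergent positive: {2, 3, 4, 5, 6} minus {2, 5} = {3, 4, 6}.
- Shared by Categories 7 and 8: {5} only.

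The rules in the same bullet then show the mismatch. The event rule mentions sub-category 5, which with Category 2 makes up Category 7. The only category named treatment-emergent negative is Category 1, and it belongs to neither 2 nor 8, so the censoring rule applies by name to no one in the displayed groups. Categories 3 (reduced), 4 (unaffected) and 6 (inconclusive) are assigned neither an event nor a censoring time. Everyone in Category 2 has the event, so a curve restricted to that category has no one to censor. The rules work only if the categories define the events and a wider population is at risk.

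**The case against.** The PGA tests are nominal, and Section 3.10 says nominal p-values are not to be used to declare significance. The antibody analysis is descriptive. That stands, and it limits the weight of the point.

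Several stronger readings are tempting, and the SAP does not support them:

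- *A treatment difference at Minimal is hidden.* It is not. Section 8.4.7 tabulates all six levels by arm and visit with shift tables, so either contiguous rate can be read off for participants with data. What cannot be read off is the imputed, model-based odds ratio and p-value.
- *Total treatment-emergent incidence is omitted.* It is not. Section 9.3.2 reports counts and percentages in each of the eight categories, including Category 7. Only the Category 7 time-to-event display is missing.
- *No one in Category 8 can have the event.* Category 5 can, and the bullet gives its titre rule. The Category 8 curve is diluted, not unrelated.
- *Counting Categories 3, 4 and 6 as non-events is itself the error.* At-risk participants without an event are ordinary in a Kaplan-Meier analysis, and they remain non-events under the correction below. The fault is that their status is unstated.

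One could also read the antibody text as two strata: first positivity in Category 2, and boosting among Baseline positives. Or one could note that {2, 3, 4, 5, 6} is the grouping Section 10.2.2 uses for adverse events on or after a first positive result. The first reading still leaves 3, 4 and 6 without a censoring rule and Category 2 with events only. The second describes participants who were ever positive, which is not the stated event.

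**Conclusion.** Both passages are wrong as written, and the consequence is limited to one nominal test variable (four comparisons) and one descriptive immunogenicity analysis. The primary endpoint, the Section 4.5 hierarchy and type I error are not affected.

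For the PGA, it is certain from the SAP that the responder set is non-contiguous. The size and direction of the error are not certain, because they depend on the intended cut and on level shares the SAP does not give. For the antibodies, Category 7 is well supported by its own definition and by the event rule in the same bullet. The conclusion that results come out wrong assumes the text is programmed literally; if it is silently reinterpreted, the fault is an undocumented analysis choice instead.

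**What to change.** - **Section 8.5:** before unblinding, replace the PGA entry with one contiguous set and give the scores: either Clear or Minimal (0–1), or Clear, Minimal or Mild (0–2). The SAP does not show which was meant, so the sponsor must decide.
- **Section 9.3.2:** change Categories 2 and 8 to Categories 2 and 7 and state that these define the events. Keep all Active Medication Set participants at risk. Censor everyone not treatment-emergent positive, including Categories 1, 3, 4 and 6, at the last available antibody result.

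The cost is one phrase in Section 8.5, and one phrase plus an at-risk and censoring sentence in Section 9.3.2. No new data are needed.

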9 PHARMACOKINETICS AND PHARMACODYNAMICS

9.1 Pharmacokinetics

Pharmacokinetic variables will be analyzed for all participants in the PK-PPS. Bimekizumab plasma concentrations will be summarized for each treatment at each scheduled visit.

PK summaries will be based on observed values. No imputation will be used. However, if plasma concentration measurements are below the level of quantification (BLQ), then for calculation of the derived statistics the result will be set to ½ of the lower level of quantification (LLOQ). Descriptive statistics including geometric mean, geometric coefficient of variation, and geometric mean 95% CI if applicable will be calculated if at least 2/3 of the values of interest are above the LLOQ. If this is not the case, only median, minimum, and maximum will be presented.

Geometric mean plasma concentration will be plotted by treatment group, and by cumulative antibody status for participants randomized to bimekizumab on linear and log linear scale. In addition, HiSCR₅₀ response (0=not achieved, 1=achieved) assessed at each PK visit (excluding Week 1) will be plotted against the visit's bimekizumab plasma concentration, separated by treatment group. Spaghetti plots of bimekizumab plasma concentrations by week from bimekizumab first dosing separated by treatment group and antibody status will be presented for participants with and without HiSCR₅₀ response at Week 16.

If the dosing for a visit is +/- 7 days out of window, then the plasma concentration from that visit and all subsequent visits will be excluded from the PK summary. In addition, if the PK sampling date is >1 day after the dosing date, then the plasma concentration from that visit will be excluded from the PK summary.

All PK concentrations collected will be listed irrespective of the dosing or sampling occurring out of window.

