2.3.2.2 Initial Treatment Period (Weeks 0-16) and Maintenance Treatment Period (Weeks 16-48)

Eligible study participants will be randomized in a 2:2:2:1 ratio as noted in the Study Schema to:

- Bimekizumab [REDACTED] from Weeks 0 to 48
- Bimekizumab [REDACTED] from Weeks 0 to 48
- Bimekizumab [REDACTED] to Week 16, continuing on [REDACTED] from Weeks 16 to 48
- Placebo to Week 16, continuing on bimekizumab [REDACTED] from Weeks 16 to 48

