3.5.8 Pharmacokinetics Per-Protocol Set

The Pharmacokinetics Per-Protocol Set (PK-PPS) will consist of study participants who received at least 1 full dose of bimekizumab and provided at least 1 quantifiable plasma concentration post-dose without important protocol deviations that would affect the PK.

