3.10 Changes to protocol-defined analyses

The MS and AMS were added as analysis sets.

The endpoints for PGI-S-HS, PGI-S-SP, PGI-C-HS, and PGI-C-SP were clarified in Section 2.2.1.3 to indicate that absolute change from Baseline will not be calculated, as these are categorical endpoints.

The HiSQOL endpoint was clarified to show that there are only 3 domains: symptoms, psychosocial, activities and adaptations and to add total score.

In Protocol Amendment 4, the secondary efficacy endpoint for skin pain response based on the worst skin pain HSSDD score is defined as a decrease from Baseline in HSSDD weekly worst skin pain score at or beyond the threshold for clinically meaningful change at Week 16. In this SAP, this endpoint is defined to include the exact value of the clinically meaningful threshold of 3, so that the skin pain response based on the HSSDD worst skin pain score is defined as at least a 3 point decrease from Baseline in HSSDD weekly worst skin pain score at Week 16 among study participants with a score of ≥ 3 at Baseline.

The following other efficacy endpoints are included in the protocol but will not be included as part of the analysis:

- Skin pain response based on the threshold for clinically meaningful change (defined as at least a 3 point decrease from Baseline in HS Symptom Questionnaire (HSSQ) weekly worst skin pain score) among study participants with a score of ≥ 3 at Baseline
- Response on other HS Symptoms (11-point numeric rating scale) - itch, drainage or oozing of HS lesions, and smell or odor
- Flare (defined as a $\geq 25\%$ increase in AN count with an absolute increase in AN count of ≥ 2 relative to Week 16) by Week 48

The calculation of nominal p-values has been added for selected efficacy endpoints. These nominal p-values are not controlled for multiplicity and should not be used to declare statistical significance.

The protocol defines the PK-PPS separately by period, but there will only be one PK-PPS for the overall study.

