9.3.2 Anti-bimekizumab antibodies

Anti-bimekizumab antibodies (ADAb) will be measured using a 3-tiered assay approach: screening assay, confirmatory assay, and titration assay. Samples confirmed as positive within the confirmatory assay will be further evaluated for the presence of neutralizing anti-bimekizumab antibodies specific to IL-17AA, IL-17FF or both. Samples will be taken at Baseline, then at study Weeks 4, 8, 12, 16, 20, 24, 36 and 48, and at PEOT and SFU timepoints.

ADAb samples are not analyzed when study participants are on a treatment other than bimekizumab. For study participants who switch from placebo to bimekizumab, samples are analyzed starting at the visit when the switch to bimekizumab occurs (Week 16). The sample at Week 16 will act as the Baseline for that treatment group.

The screening cut point will be used to determine the status of anti-bimekizumab antibodies in the test sample as Positive Screen (PS) or Negative Screen (NS). For samples presenting anti-bimekizumab antibody levels that are PS, a further confirmatory assay will be performed, and the result of which will be reported as either Positive Immunodepletion (PI) or Negative Immunodepletion (NI).

ADAb status for each sample will be derived as follows:

- Sample values that are either NS, or PS and NI and where the bimekizumab concentration is less than the validated ADAb assay drug tolerance limit will be defined as anti-bimekizumab antibody negative.
- Sample values that are either NS, or PS and NI and where the bimekizumab concentration exceeds the validated ADAb assay drug tolerance limit will be defined as inconclusive.

- Sample values that are PS and PI will be defined as ADAb positive (regardless of availability of a titer value)
- Missing or non-evaluable samples will be defined as missing

Positive immunodepletion samples will be titrated, and the ADAb titer (reciprocal dilution factor including minimum required dilution) will be reported. Subsequently, PI samples will also be subject to a neutralizing assay to evaluate the potential of ADAb to neutralize the target binding of bimekizumab (IL-17AA or IL-17FF or both) in vitro.

Cumulative ADAb status will be derived as follows:

The ADAb status (positive, negative or missing) will be considered in a cumulative manner at each time point.

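### Concentration and antibody plots group the placebo-to-bimekizumab arm by a Week 16 HiSCR50 response recorded before any bimekizumab, so in that arm they cannot relate exposure or antibodies to response

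*SAP*

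**What the plan says.** Three planned displays group participants by HiSCR50 at Week 16:

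- Section 9.1 plans "Spaghetti plots of bimekizumab plasma concentrations by week from bimekizumab first dosing separated by treatment group". The same sentence then divides these plots by response: "and antibody status will be presented for participants with and without HiSCR₅₀ response at Week 16".
- Section 9.3.2: "Individual plots of plasma bimekizumab concentrations/ ADAb titer both plotted on the Y-axes by visit (x-axis) for the full treatment period", again for Week 16 responders and nonresponders.
- Section 9.3.2: HiSCR50 "responders at Week 16, separated by treatment group, as a function of ADAb titer will be presented graphically".

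The fourth randomized arm is described in Section 2.3.2.2 as "Placebo to Week 16, continuing on bimekizumab" (the dose is redacted). For antibody results, Section 9.3.2 makes Week 16 the starting point of this arm: "The sample at Week 16 will act as the Baseline for that treatment group".

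The pharmacokinetic set takes participants who "received at least 1 full dose of bimekizumab and provided at least 1 quantifiable plasma concentration post-dose" and have no important deviation affecting PK (Section 3.5.8). Section 3.10 adds that "there will only be one PK-PPS for the overall study". The antibody analyses run on the Active Medication Set, which requires at least one dose of bimekizumab (Sections 3.5.5 and 9.3.2).

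**The concern.** A plot of drug level or antibody titer grouped by response is meant to let a reader see whether the two move together. That requires a response that could have been influenced by the drug level or the titer. In the placebo-to-bimekizumab arm the grouping response closes at the visit where bimekizumab begins.

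The plan resets other quantities for this arm. Relative day is also counted from first bimekizumab dose (Section 3.2.1), the antibody Baseline moves to Week 16 (Section 9.3.2), and the time axis of the Section 9.1 spaghetti plots starts at first bimekizumab dose. The response visit is not reset, and no reason is given.

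What is at stake is interpretation. Someone looking at this arm's panels could conclude that exposure or antibodies have no bearing on response, or see a pattern with no such meaning.

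**Working it through.** **1. Is the arm in the figures?** Yes. Anyone who switched from placebo and received a full bimekizumab dose can enter the single pharmacokinetic set, and one dose is enough for the Active Medication Set. Section 9.1 does restrict one display to participants randomized to bimekizumab, but that restriction belongs to the geometric-mean plot by antibody status. The spaghetti-plot sentence has none.

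**2. Which Week 16 is meant?** Section 8.2.1 derives HiSCR50 by study visit, and nothing in Section 9 redefines Week 16 as 16 weeks from first bimekizumab dose. A programmer would use the study visit.

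**3. Order of events in this arm.**

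| Display | Response used | Drug or antibody data in this arm |
|---|---|---|
| 9.1 spaghetti plots | Study Week 16, after 16 weeks of placebo | Concentrations from first bimekizumab dose at Week 16 onward |
| 9.3.2 individual plots | Same | Concentrations and titers on bimekizumab, all after Week 16 |
| 9.3.2 responders by titer | Same | Titer visit not stated: either the Week 16 Baseline sample or later samples |

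No row pairs an on-bimekizumab measurement with a response it could have affected.

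**4. Separation by arm.** The spaghetti plots and the response-by-titer graph are stated to be separated by treatment group. The individual concentration/titer plots are not, so as written their responder set may hold placebo responders and bimekizumab responders together.

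**5. Scale.** Inputs from Section 2.4 and Table 2-1: 490 randomized, 70 to placebo; HiSCR50 at Week 16 of 0.25 on placebo, and 0.50 (N=140) and 0.60 (N=280) on bimekizumab.

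These rates reproduce the plan's stated power of 0.90 for 0.50 versus 0.25 with 140:70 at two-sided 0.025:
- Pooled rate = (70×0.25 + 140×0.50)/210 = 0.4167.
- Null SE = √(0.4167×0.5833×(1/70 + 1/140)) = 0.0722.
- Alternative SE = √(0.25×0.75/70 + 0.50×0.50/140) = 0.0668.
- Power = Φ((0.25 − 2.241×0.0722)/0.0668) = 0.907.

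The stated power is not in dispute; this only confirms that the rates are read correctly.

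- Share of the trial in this arm: 70/490 = 14.3%.
- Grouped as responders on placebo outcome: 0.25×70 = 17.5; as nonresponders: 0.75×70 = 52.5.

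**6. Illustration of how far the grouping may depart from on-drug response.** Assume, beyond what the SAP states, that all 70 enter the figures and that the arm later reaches a HiSCR50 rate p of 0.50 to 0.60.
- If every placebo responder also responds on drug, the discordant number is 70×(p − 0.25): 17.5 for p = 0.50 and 24.5 for p = 0.60. This is the minimum.
- If the two responses are independent, it is 70×(0.25(1 − p) + 0.75p): 35.0 for p = 0.50 and 38.5 for p = 0.60.

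**The case against.** The strongest reply is that little depends on these figures. They are descriptive and nothing in them is tested or estimated. Two of the three are separated by treatment group, so the other arms' panels in those two are clean. The relation on drug is also shown elsewhere: Section 9.1 plots HiSCR50 at each PK visit (Week 1 excepted) against that visit's concentration, and Section 4.8 summarizes HiSCR50 by visit and antibody positivity through the Maintenance Treatment Period. A reader who knows the arm can see that Week 16 comes before drug, the more so in the individual plots, which run by study visit. All of this stands, and it makes the point minor. It does not make the grouping informative in this arm, and it does not answer the missing arm separation in the individual plots.

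Two stronger readings are tempting and not supported:

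- A reader might infer that the response-by-titer graph sets later titers against an earlier response. The SAP does not say which visit's titer is used. If only titers up to Week 16 enter, this arm contributes at most a pre-dose Baseline value. The visit is unspecified; a wrong pairing is not shown.
- A reader might take the 17.5 to 38.5 discordant participants as an error count. They are not one. The panels are labelled by Week 16 response, the later rates are borrowed from other arms, the SAP gives no joint distribution of the two responses, and fewer than 70 may qualify.

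**Conclusion.** The point holds and is minor. In three descriptive displays the placebo-to-bimekizumab arm, 14.3% of those randomized, is grouped by a placebo response recorded before any bimekizumab. In that arm these displays cannot show how concentration or antibodies relate to response. This follows from the definitions and does not depend on the discordance figures. It rests on reading Week 16 as the study visit, which is the only definition the SAP gives.

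It would be wrong to infer that the exposure-response or antibody-response displays fail as a whole, or that any efficacy conclusion or the type I error rate is touched. The other arms' panels, the same-visit plot and the antibody subgroup summaries remain sound.

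**What to change.** In Sections 9.1 and 9.3.2, either leave the placebo-to-bimekizumab arm out of the Week 16 response split in these three displays, or group that arm by HiSCR50 at Week 48 and label the panels so. Week 48 suits because antibody sampling is scheduled then. Week 32, 16 weeks after first bimekizumab dose, suits less: Section 9.3.2 schedules no antibody sample at that visit, and the latest earlier one is Week 24.

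State that the individual concentration/titer plots are separated by treatment group. State also that the response-by-titer graph uses only titers from samples taken on bimekizumab, up to and including the response visit.

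The cost is a few sentences of SAP text and one grouping variable in the figure programs. The downside is small: the response visit differs between arms and has to be labelled, or one arm's panel is dropped.
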